## Protocol Amendment 01 (20-Dec-2021)

### Amendment Rationale

As of the date of release of this protocol amendment, 14 subjects have been enrolled in the study (9 dosed).

The main purpose of the amendment is to update the inclusion criterion on definition of high risk prostate cancer per D'Amico classification to also include patients with clinical stage T2c or higher at initial diagnosis (instead of T2c only) as those are considered high risk as well per D'Amico classification. Other clarifications and corrections of discrepancies or errors have been implemented across protocol. All changes implemented are detailed below with their justification.

The changes described in this amended protocol require IRB/IEC approval prior to implementation.

A copy of this amended protocol will be sent to the Institutional Review Board (IRBs)/Independent Ethics Committee (IECs) and Health Authorities.

The changes herein do not affect the Informed Consent.

Main changes implemented in the protocol amendment		
Section	Change	Description and rationale
Protocol summary Section 5.1 Section 2.1 Section 8.2	Update of Inclusion criterion #1	Modified inclusion criterion (numbered 1a) to include patients with clinical stages T2c and higher for prostate cancer as D'Amico classification is also considering such patients as high risk.
Protocol summary Section 5.2 Section 6.2.2	Removal of exclusion criterion #6 and update of exclusion criterion #5 and clarification that LHRH analogues include LHRH agonists or antagonists	Exclusion criterion #6 is removed as the targeted population for this study is subjects who are newly diagnosed with prostate cancer and did not receive any prior androgen-deprivation therapy (ADT). Exclusion criterion #5 was updated accordingly (numbered 5a) to exclude any prior ADT including LHRH analogues (agonists or antagonists). Section 6.2.2 was also updated to clarify that LHRH analogues include LHRH agonists or antagonists.
Protocol summary Section 2.1 Section 3 Section 8.3.2	Update of Surgery timing	Updated to mention that surgery will be performed up to 6 weeks after but not sooner than 48 hours after the completion of the [  F]CTT1057 PET/CT scan. This change ensures all patients will go at least through a 2-day period to check their safety after PET scan without being confounded by the effects of surgery.

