Study population	
Male participants ≥ 18 years of age, with newly diagnosed high-risk PCa who are candidates for radical prostatectomy (RP) and extended lymph node resection as per SoC.
 
Approximately 195 participants will be enrolled to ensure that at least 156 participants are evaluable (i.e. have both an evaluable PET/CT scan and histopathology assessment and have not received any prohibited systemic antineoplastic therapy before the completion of PET/CT and surgery), which will be required for the calculation of the co-primary endpoints.

Inclusion criteria	
 
Signed informed consent must be obtained prior to participation in the study
 
Untreated high risk biopsy-proven PCa patients according to D'Amico classification (Stage ≥ T2c or Prostate Specific Antigen (PSA) level >20ng/ml or Gleason score ≥8)
 
Scheduled or planned radical prostatectomy and extended pelvic lymph node resection up to 6 weeks after the investigational PET/CT scan followed by histopathology assessment
 
Eastern Cooperative Oncology Group (ECOG) performance status 0-2
 
Participants must be adults ≥ 18 years of age
 

Exclusion criteria	
 
Inability to complete the needed investigational and standard-of-care imaging examinations due to any reasons (severe claustrophobia, inability to lie still for the entire imaging time, etc.)
 
Any additional medical condition, serious intercurrent illness, concomitant cancer or other extenuating circumstance that, in the opinion of the Investigator, would indicate a significant risk to safety or impair study participation, including, but not limited to, current severe urinary incontinence, hydronephrosis, severe voiding dysfunction, need of indwelling/condom catheters, New York Heart Association class III or IV congestive heart failure, history of congenital prolonged QT syndrome,
 

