**Medical history:**

- Date of diagnosis of PCa (diagnostic criteria is to be reported also in the eCRF) ((Stage  $\geq$  T2c or PSA level  $>20$ ng/ml or Gleason score  $\geq 8$ )
- Results of digital rectal examination (cT1c, cT2a, cT2b, cT2c, cT3)
- Ongoing medical conditions, symptoms and diseases which are recorded on the Medical History eCRF should include the toxicity grade when applicable
- Concomitant medications of the last 30 days prior to enrollment (dose, dates)
- Other important medical, surgical, and allergic conditions that could have an impact on the participant's evaluation) / current medical conditions (e.g. all relevant current medical conditions which are present at the time of signing informed consent).

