### 2.2.1 Subgroup of interest

The co-primary efficacy endpoints will be summarized by the following subgroups:

(a) PSA level at baseline (from central laboratory)

- $PSA \le 20 \text{ ng/mL}$
- PSA > 20 ng/mL

(b) Gleason Score

- Grade Group 1 Gleason score  $\leq 6$
- Grade Group 2 Gleason score 7 (or 3 + 4 = 7)
- Grade Group 3 Gleason score 7 (or 4 + 3 = 7)
- Grade Group 4 Gleason score 8
- Grade Group 5 Gleason score 9 or 10

(c) Number of pelvic lymph nodes (PLNs) dissected during the surgery

- PLNs < 12
- $PLNs \ge 12$

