#### Diagnosis and extent of cancer

Diagnosis and extent of cancer will be summarized and listed. This analysis will include the following: PSA level at time of initial diagnosis (ng/mL), primary tumor clinical stage (i.e. T2c or less, T3, T3a, T3b, T4 and Tx), biopsy predominant histology/cytology, percentage of each histological type/pattern, biopsy Gleason score (i.e.  $\leq 6$ , 7 (3+4), 7 (4+3), 8, and 9 or 10), time since initial diagnosis (in months). Note: biopsy Gleason score will be displayed along with the score details for each score combination in the table.

Derivation:

Time since initial diagnosis to PET scan (in months) = (date of PET scan – date of first prostate cancer diagnosis + 1) / 30.4375

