#### 2.5.6 Supplementary analyses

As supplementary analyses performed for the EFF, patient-level sensitivity and region-level specificity and the corresponding 95% CIs will be obtained from a covariate-adjusted logistic regression model. Candidate covariates include categorized PSA level at baseline, diagnostic biopsy Gleason score, and categorized number of PLNs dissected as given below.

- PSA level
  - $\circ$  PSA  $\leq$  20 ng/mL
  - $\circ$  PSA > 20 ng/mL
- Gleason Score
  - Grade Group 1 Gleason score  $\leq 6$
  - Grade Group 2 Gleason score 7 (or 3 + 4 = 7)
  - Grade Group 3 Gleason score 7 (or 4 + 3 = 7)
  - Grade Group 4 Gleason score 8
  - Grade Group 5 Gleason score 9 or 10
- Number of PLNs dissected
  - $\circ$  Number of PLNs < 12
  - $\circ$  Number of PLNs >= 12

Estimates of patient-level sensitivity and region-level specificity and the corresponding 95% CIs will be obtained from the logistic regression model adjusting for covariates. The p-values from the Type III tests for each candidate covariate in the full model will be provided. The patient-level sensitivity and region-level specificity (and their 95% CIs) for each level of the covariates estimated from the full model including all candidate covariates as well as the final model including only statistically significant covariates (p-value < 0.05) will be displayed. In the case that there are no statistically significant covariates identified from the full model, patient-level sensitivity and region-level specificity (and their 95% CIs) for the unadjusted logistic regression model will be provided.

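### Clinical T stage helps define who is eligible but is missing from the planned subgroups and adjusted models, so PSA and Gleason contrasts could be confounded by stage

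*Protocol*

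**What the plan says.** Eligibility (Protocol summary and 5.1) requires high-risk disease by stage, PSA or Gleason: "Untreated high risk biopsy-proven PCa patients according to D'Amico classification (Stage ≥ T2c or Prostate Specific Antigen (PSA) level" above 20 ng/ml, or Gleason at least 8. The stated main purpose of Amendment 01 was to widen the stage criterion, "to also include patients with clinical stage T2c or higher at initial diagnosis (instead of T2c only").

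SAP 2.2.1 states: "The co-primary efficacy endpoints will be summarized by the following subgroups". It then lists PSA (cut at 20 ng/mL), five Gleason grade groups and nodes dissected (under 12, or 12 and more). The PSA variable is "PSA level at baseline (from central laboratory").

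SAP 2.5.6 uses the same three factors for the adjusted logistic models: "Candidate covariates include categorized PSA level at baseline, diagnostic biopsy Gleason score, and categorized number of PLNs dissected as given below". Type III p-values are printed for the full model, and "the final model including only statistically significant covariates (p-value < 0.05) will be displayed". The two model equations in SAP 5.4.1 contain PSA, Gleason and node-count terms only.

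Stage is available. Protocol 8.2 collects "Results of digital rectal examination (cT1c, cT2a, cT2b, cT2c, cT3"), and SAP 2.3.2 tabulates "primary tumor clinical stage (i.e. T2c or less, T3, T3a, T3b, T4 and Tx"). No reason is given for leaving it out of the subgroups and models. Protocol 12.4.6 gives the purpose of the subgroup analyses as assessing homogeneity across demographic and baseline disease characteristics.

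**The concern.** Two of the three characteristics that define the population are analysed and the third is not. Because one criterion suffices, selection ties the three together: men who are low on PSA and Gleason are in the trial because of stage, while men high on either may have any stage. The reference groups for the PSA and Gleason comparisons therefore tend to have more advanced stage.

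If stage also affects whether the scan detects disease, given PSA and Gleason, a PSA or Gleason contrast that ignores stage mixes two effects. It could show lower sensitivity in high-Gleason men when Gleason has no effect, or shrink a real increase. The p < 0.05 rule could then keep or drop a covariate for the wrong reason. Stage is not a candidate, so no planned model would show this. The baseline table would not help either: its lowest category pools T2c, which meets the stage criterion, with T1c–T2b, which do not.

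**Working it through.** **1. The plan's own figure.** For n = 156 and null sensitivity 0.50, the smallest count with one-sided exact tail at most 0.025 is 91 (tail 0.0225). Power at 0.63 is 0.901, and 156/(1 − 0.20) = 195. The stated size and 90% power reproduce, and nothing in them depends on stage. The documents give no figure for the PSA or Gleason analyses, so the inputs below are assumptions.

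**2. Stage mix produced by the rule.** Assume that before eligibility 40% have stage ≥ T2c, 25% PSA > 20 and 40% Gleason ≥ 8, independently. Among eligible men:

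- Gleason ≤ 7: share ≥ T2c = 0.40/[1 − 0.60 × 0.75] = 0.40/0.55 = 72.7%. Gleason ≥ 8: 40%.
- PSA ≤ 20: 0.40/[1 − 0.60 × 0.60] = 0.40/0.64 = 62.5%. PSA > 20: 40%.
- PSA ≤ 20 and Gleason ≤ 7: 100%.

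Positive correlation among the criteria narrows this. At latent correlation 0.4 the Gleason shares are 78% and 56%, and the PSA distortion nearly vanishes. Source prevalences from 30/20/30% to 50/30/50% give, for PSA ≤ 20 versus > 20, 59–67% versus 30–50% under independence. With pairwise odds ratio 3 they give 63–70% versus 55–73%, and one scenario reverses.

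**3. Effect on a one-way contrast if only stage matters.** High group minus low group = (difference in stage share) × (difference in sensitivity by stage), at zero correlation:

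| Sensitivity ≥ T2c vs < T2c | Gleason | PSA |
|---|---|---|
| 0.75 vs 0.45 | (0.400 − 0.727) × 0.30 = −9.8 points | (0.400 − 0.625) × 0.30 = −6.8 points |
| 0.66 vs 0.58 | −0.327 × 0.08 = −2.6 points | −0.225 × 0.08 = −1.8 points |
| equal | 0 | 0 |

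**4. False significance in the sensitivity model.** Simulated with 156 men, prevalences 40/25/40%, only stage acting, and a logistic model in PSA and Gleason without stage, tested at 5%. Where three values are given they are for latent correlation 0, 0.2 and 0.4:

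| Sensitivity by stage | PSA term | Gleason term |
|---|---|---|
| 0.75 vs 0.45 | about 21, 11, 6% | about 32, 23, 14% |
| 0.70 vs 0.50 | 5–12% | 8–16% |
| 0.66 vs 0.58 | 4–7% | 4–7% |
| no stage effect | nominal | nominal |

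The first row rests on 800 replicates, so its largest standard error is about √(0.32 × 0.68/800) = 1.6 points. In that row's scenario, adding a stage term brings both odds ratios back to about 1.0, with interval coverage of 92–95%.

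**5. Masking a real effect.** Large-sample fit with true odds ratio 2 for both PSA and Gleason, overall sensitivity 0.63, prevalences 30/20/30% to 50/30/50%, and pairwise odds ratio among the criteria 1 to 3:

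| Stage odds ratio | PSA, stage omitted | Gleason, stage omitted | Both, stage included |
|---|---|---|---|
| 1 | 2.00 | 2.00 | 2.00 |
| 2 | 1.43–2.00 | 1.38–1.74 | 2.00 |
| 3 | 1.18–1.98 | 1.11–1.59 | 2.00 |

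**6. Limits.** Steps 4 and 5 split Gleason at 8 (the SAP has five groups) and omit the node-count term. No eligible man is below T2c with PSA ≤ 20 and Gleason ≤ 7, so full recovery with stage included depends on additivity, which these calculations assume. The specificity model was not simulated. With 156 evaluable men, 70% node-negative, specificity 0.85 and one region per man (an assumption), it would have 156 × 0.70 × 0.15 ≈ 16 false positives. That is 16.4/6 = 2.7 per slope now and 16.4/7 = 2.3 with one more.

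**The case against.** The strongest reply is that the plan never promises a PSA or Gleason effect independent of stage. The estimand population is men who meet the eligibility rule, and SAP 2.2.1 summarises the endpoints by subgroup. A PSA difference that partly reflects stage mix is a true description of those men. In re-simulation of the strong-effect scenarios, intervals for the PSA and Gleason coefficients covered their eligible-population values (stage omitted) 94–96% of the time. This stands: what suffers is the reading of a contrast as a separate PSA or Gleason effect, not the validity of the intervals or p-values for the association in eligible men.

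Further points also stand:

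- No part of the documents links stage to detection. The only hint about a predictor concerns PSA: in Protocol 1.1, the one Phase I primary-staging miss had the lowest PSA in the cohort. The 0.75 versus 0.45 scenario is a strong one.
- The all-stage cell may not be exact in the data. Subgroup PSA is the central baseline value, PSA at diagnosis is a separate variable in SAP 2.3.2, and the Amendment 01 summary says eligibility can rest on local laboratory results.
- The SAP displays p-values and predicted sensitivities and specificities rather than odds ratios, so step 5 shows the mechanism and not a planned output.
- Individual diagnosis data are listed, and the SAP history attributes the grouping of stage to steering-committee comments. The coarse category is not concealment.
- Forcing stage into the specificity model whatever its p-value is hard to defend with so few expected false positives.

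None of this supplies a reason to omit an eligibility-defining, already collected factor from analyses meant to examine homogeneity across baseline disease characteristics.

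**Conclusion.** A cheap improvement. The omission is plain from the documents, and the enrichment of low-PSA and low-Gleason men for stage ≥ T2c follows approximately from the eligibility rule. It weakens, and for PSA can disappear or reverse, as the criteria become positively correlated. Whether it confounds anything depends on a stage effect that the documents do not quantify. Under the stated assumptions the consequence runs from no excess, through 4–7% false significance at an eight-point stage difference, to about 6–21% (PSA) and 14–32% (Gleason) at a thirty-point difference. Gleason is the more exposed term.

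A reader might infer that the eligibility rule by itself biases the PSA and Gleason estimates, or that the printed p-values and intervals are invalid. Neither follows. Distortion of a separate PSA or Gleason effect needs the rule, the omission of stage and a stage effect together, and the subgroup proportions remain correct for eligible men. A reader might also infer that the trial's conclusion is at risk. It is not: the success rule in SAP 2.5.2 uses unadjusted exact binomial intervals per reader, and neither they nor the sample size involve these models.

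**What to change.** - SAP 2.2.1: add a clinical-stage subgroup (< T2c, T2c, ≥ T3), with Tx listed.
- SAP 2.5.6 and 5.4.1: add clinical stage (≥ T2c versus < T2c) as a candidate covariate under the existing selection rule. For the sensitivity model, also show the PSA and Gleason results with stage included. Do not require stage to be kept in the specificity model, where false positives may be few.
- SAP 2.3.2: split the lowest stage category into < T2c and T2c.
- Footnote the PSA and Gleason subgroup tables as conditional on an eligibility rule that any one of three criteria satisfies.

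Cost: SAP wording, one more subgroup, one more table row and one more slope, all from data already collected. Intervals in a supplementary model become slightly wider.

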# 1 Introduction

## 1.1 Background

### Prostate-specific membrane antigen (PSMA) and prostate cancer

Prostate-specific membrane antigen (PSMA) is a transmembrane protein, also known as folate hydrolase or glutamate carboxypeptidase II. PSMA is highly overexpressed in the tumor cells of prostate adenocarcinomas (Mannweiler et al 2009, Hupe et al 2018, Bravaccini et al 2018) and has also been reported to be overexpressed in tumor cells and tumor-vasculature of endometrial and ovarian cancer (Wernicke et al 2017), and mainly in tumor-vasculature of a variety of other cancer types such as breast (Tolkach et al 2018), colorectal, gastric (Haffner et al 2009), glioblastoma (Wernicke et al 2011, Tanjore Ramanathan et al 2020), kidney (Spatz et al 2018), liver (Tolkach et al 2019), lung (Wang et al 2015, Schmidt et al 2017) and pancreatic cancer (Stock et al 2017). PSMA has restricted and several hundred-fold lower expression than PCa cells in some normal tissues such as the duodenal mucosa, proximal renal tubules, and salivary glands (Bostwick et al 1998, Ghosh and Heston 2004).

From all the above named PSMA-overexpressing tumors, PCa is the one in which the role of PSMA has been more extensively studied. PCa remains the cancer with the second highest mortality in the United States (US), and the third leading cause of cancer-related death in Europe in men (Siegel et al 2017, Malvezzi et al 2019). It also remains the most diagnosed cancer with an estimated increase of 9,960 new cases with a total of 164,690 in 2018 (Siegel et al 2018) to 174,650 in 2019 (Siegel et al 2019). Most of the diagnosed cases are in more developed regions due to the use of PSA testing, but there is only modest variation in mortality rates globally which is driven by metastatic, and often castration-resistant disease (Bray et al 2013). Subsequent treatment is multifaceted and may involve observation, surgery (prostatectomy), radiation therapy (external beam or brachytherapy), hormonal therapy, chemotherapy, and in the near future, radioligand therapy (Roscigno et al 2005, Jani 2006). PSMA overexpression correlates with advanced, high-grade, metastatic, androgen-independent disease (Ross et al 2003). The differential expression of PSMA from tumor to non-tumor tissue has resulted in numerous targeted strategies involving both disease localization using PSMA-PET imaging as well as therapeutic intervention. Correct identification of disease location and extent determines treatment decisions for patients with PCa. Identification of distant metastatic disease at the initial diagnosis of PCa is important in planning PCa management. There is increasing evidence that primary landing sites for PCa lie outside the template of an extended pelvic lymph node dissection (ePLND). Primary lymph node landing sites outside an ePLND have been reported in 47.7% of men with suspected node-positive disease on [Ga]Ga-PSMA PET/CT (Yaxley et al 2019a). This is very important, as the morbidity of an ePLND could be avoided, given the change in expectation of management from one of curative intent, to management that will require a multimodality approach after treatment of the prostate primary (Yaxley et al 2018, Yaxley et al 2019b). It is relevant, therefore, to detect smaller lesions as early as possible. With the emergence of PSMA-targeted radioligand therapy, in addition to early diagnosis accurate PSMA-positivity detection is needed to determine the future use of radioligand therapy.

## Positron Emission Tomography (PET) imaging in PCa

The usual diagnostic tools for PCa include PSA testing, digital rectal palpation, transrectal ultrasound, prostate biopsy, and histopathologic examination (Schwarzenböck et al 2012, Smith et al 2016, Prasad et al 2016). Additionally, further imaging techniques such as Magnetic Resonance Imaging (MRI), bone scintigraphy, CT, and [F]Fluorodeoxyglucose (FDG), [F]Choline, [C]Choline and the most recently approved [F]-fluciclovine (Nanni et al 2016, Odewole et al 2016) PET/CT are used for staging primary PCa and restaging biochemical recurrences (Schwarzenböck et al 2012). CT and MRI are the standard of care imaging procedures for measuring tumors at baseline and lesions selected for response assessment as per Response Evaluation Criteria In Solid Tumors (RECIST) criteria 1.1 (Eisenhauer et al 2009). However, these imaging modalities have shown limited yielding in the staging of PLN in patients with PCa. A meta-analysis showed pooled sensitivities of 0.42 (95% CI 0.26-0.56) for CT, and of 0.39 (95% CI 0.22-0.56) for MRI (Hövels et al 2008). Therefore, more sensitive and accurate imaging tests than the currently available Standard of Care (SoC) examinations are needed (Hricak et al 1987, Shinohara et al 1989, Scheidler et al 1999, Blomqvist et al 2014). Novel PET radiotracers promise to overcome this limitation. PET imaging is an enticing choice as it offers the potential to both stage patients and provide insight into tumor biology. Among the various PET probes available, Ga-labeled ligands of the PSMA were associated with unprecedented accuracy and effect on treatment in several meta-analyses of retrospective studies (Perera et al 2016, Han et al 2018, Von Eyben et al 2018). Recent studies reported that Ga-labeled PSMA PET/CT has excellent detection rates for lymph node metastases, skeletal metastases, local relapses, and soft-tissue metastases compared with other PET tracers such as F- and C-labeled choline derivatives (Afshar-Oromieh et al 2013, Afshar-Oromieh et al 2014, Ceci et al 2015, Eiber et al 2015, Budäus et al 2016). Since its introduction in 2012, [Ga]Ga-PSMA-11 is the most studied PSMA PET agent to date. It has been widely used in clinical practice on a compassionate use basis and reported in prospective studies and numerous retrospective case series (Afshar-Oromieh et al 2015, Eiber et al 2015, Morigi et al 2015, Meredith et al 2016, Sachpekidis et al 2016, Afshar-Oromieh et al 2017, Berliner et al 2017, Gupta et al 2017, Hope et al 2017, Sanli et al 2017, Schmuck et al 2017, Derlin et al 2018, Grubmüller et al 2018, Kranzbühler et al 2018, Lengana et al 2018, Rauscher et al 2018, Fendler et al 2019), and it has been recently approved in the USA (December 2020) as a radioactive diagnostic PET imaging agent in men with PCa with suspected metastasis who are candidates for initial definitive therapy, or with suspected recurrence based on elevated serum PSA level ([Ga]Ga-PSMA-11 USPI). However, despite the diagnostic accuracy of [Ga]Ga-PSMA-11, its practical use at scale is limited by the short half-life of Ga, which requires radiolabeling in close proximity to the point of care. Moreover, the yield of currently available Ga generators limits the manufacturing of the number of doses required to address the growing population of PCa patients. This gap between the unmet need and availability is expected to widen as radio-ligand therapy options are available for treatment. While solid targetry using cyclotrons (currently unapproved for clinical use) can generate greater quantities of Ga, and thereby more doses, the geographical reach of the few cyclotrons coupled with the short half-life of Ga would still leave this need unaddressed.
